5.0 Inclusion and Exclusion Criteria/ Study Population

College students aged 18-25 will be recruited from Arizona State University (no participants will be recruited until an inter-institutional agreement is signed by Arizona State University, submitted as an amendment to the MUSC IRB and approved by the MUSC IRB) to complete questionnaires regarding their attitudes and behaviors related to alcohol use, sexual assault victimization, sexual assault perpetration, and bystander intervention. Human subjects are also being recruited to participate in an open pilot and a randomized pilot to determine usability as well as estimate effect size for a larger grant. In Aim 1a, we will recruit 750 college students aged 18-25 (n= 250 women; n=250 men; n=250 sexual/gender minorities) from both Arizona State University (data already collected and have de-identified dataset) and Georgia State University. In this aim, human subjects are needed to assess setting-specific normative attitudes and behavior for alcohol use and sexual assault to incorporate into the intervention content. Aim 1b includes alpha testing of a workbook version of the intervention, which will include interviews with key stakeholders (college administrators and 15 students) to inform programming content at both Arizona State University (data already collected and have de-identified dataset) and Georgia State University. In Aim 2, we will recruit 30 students (10 from each risk group (cisgender heterosexual men, cisgender heterosexual women, and sexual/gender minorities) who engage in heavy episodic drinking in the past month to participate in an open pilot trial to obtain usability feedback to integrate into the intervention content. In Aim 3, which will only be collected from Arizona State University, we will recruit 54 students who engage in heavy episodic drinking in the past month from each risk group (cisgender heterosexual men, cisgender heterosexual women, and sexual/gender minorities) for a total of 162 students aged 18-25 to participate in a randomized pilot trial. Aim 3 focuses on observing effect sizes and estimating the variability using a 3-month follow-up design to design a larger study for an R01 application. In this IRB application at Georgia State University, a total of 967 participants will be recruited (Aim 1a = 750 students from GSU, Aim 1b = 25 [25 students and 10 administrators] from GSU, Aim 2 = 30 students from GSU, Aim 3 = 162 students from ASU).

Inclusion criteria for Aim 1a:

- 1) 18-25 years old
- 2) Current college student at Georgia State University
- 3) Valid Georgia State University email address

Inclusion criteria for Aim 1b (students):

- 1) 18-25 years old
- 2) Current college student at Georgia State University
- 3) Identify as cisgender heterosexual male, cisgender heterosexual female, or sexual/gender minority
- 4) Valid Georgia State University email address

- 5) Endorse engaging in heavy episodic drinking at least once in the past month on the screening survey

Inclusion criteria for Aim 1b (administrators):

- 1) Current administrator role at Georgia State University
- 2) Individuals must make either final or preliminary decisions regarding alcohol and/or sexual assault programming on the Georgia State University campus

Inclusion criteria for Aim 2:

- 1) 18-25 years old
- 2) Current college student at Georgia State University
- 3) Valid Georgia State University email address
- 4) Endorse engaging in heavy episodic drinking at least once in the past month on the screening survey

Inclusion criteria for Aim 3:

- 1) 18-25 years old
- 2) Current college student at Arizona State University
- 3) Valid Arizona State University email address
- 4) Endorse engaging in heavy episodic drinking at least once in the past month on the screening survey

Exclusion criteria for Aims 1, 2, and 3: There are no exclusion criteria aside from not meeting inclusion criteria.

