1.0 Objectives / Specific Aims

Aim 1: Modify Alcohol and Sexual Assault Prevention (ASAP) content to an eHealth format to include personalized content for each risk group (1. cisgender heterosexual men; 2. cisgender heterosexual women; and 3. sexual and gender minorities).

Aim 1a: Assess normative behaviors ($n = 750$) regarding alcohol use and SA for feedback from Arizona State University (already completed and de-identified data being analyzed) and Georgia State University.

Aim 1b: Adapt and assess initial acceptability of a workbook version of the intervention content among key stakeholders (college administrators and students from each risk group [$n=5$ from each group]) from Arizona State University (already completed and de-identified data being analyzed) and Georgia State University.

Aim 2: Open Pilot Trial. Obtain usability of ASAP among 30 students who engage in HED (10 from each risk group) in an open pilot trial at Arizona State University (already completed and de-identified data being analyzed) and Georgia State University.

Aim 3: A pilot to assess effect size and variability for planning a randomized trial in the future. This Aim will only be conducted at Arizona State University. Randomize students who engage in HED to ASAP or control condition to observe preliminary effect sizes and estimate the variability using a 3-month follow-up. Sample size was determined to estimate the variability within a reasonable margin of error. This calculation also accounted the low base rates of SA and 20% attrition. This led to a sample size of 162 students ($n=54$ from each risk group).

By accomplishing these aims, we will have established the research team, programming, feasibility and preliminary efficacy of the research protocol. If promising, this study will lay the groundwork for an R01 application to test the efficacy of ASAP.

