Bystander intervention component (all risk groups): Bystander intervention content is already developed for in person delivery modes and will be included in both the women- and men-specific ASAP interventions. The bystander intervention approach focuses on targeting SA perpetration by eliciting bystanders to intervene in potential SA situations and target social norms for SA. This content will be adapted to a mHealth delivery mode from the discussion-based module of the Men's Workshop. This module includes university- specific feedback regarding perceived and actual social norms of men engaging in insensitive behavior towards women (i.e., using the word "slut" to insult a woman or men joking about having sex with a woman), psychoeducation regarding barriers to intervening with potential SA situations, and practice scenarios using effective intervention strategies, all of which are easily translatable to mHealth delivery modes.

Support for this approach: Bystander intervention as incorporated with the Men's Program has been studied by [name] as described above.

Adaptation for current study: The adaptation strategy will be the same as the perpetration prevention content described above.

Control Group: The control group will be compared to those assigned to the intervention (intervention components described above. The control group will be an assessment only control, meaning that they will only complete the assessment at baseline instead of receiving an intervention.

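### Aim 3 has no exclusion for students already exposed to the intervention in Aims 1b or 2 at Arizona State, which may attenuate its effect estimate

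*Protocol*

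**What the plan says.** Protocol Section 5.0 closes its eligibility lists with one rule for all aims: "Exclusion criteria for Aims 1, 2, and 3: There are no exclusion criteria aside from not meeting inclusion criteria". The Aim 3 inclusion list has four items: age 18-25, "Current college student at Arizona State University", a valid Arizona State email address, and "Endorse engaging in heavy episodic drinking at least once in the past month on the screening survey".

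Section 1.0 says of Aim 3: "This Aim will only be conducted at Arizona State University". It places the Aim 2 test of ASAP "in an open pilot trial at Arizona State University (already completed and de-identified data being analyzed) and Georgia State University", and says the same of the Aim 1b workbook review. Section 5.0 repeats that the Arizona State data for Aim 1b are already collected and de-identified.

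The Aim 3 paragraphs of Section 8.0 (recruitment) and Section 10.0 (procedures) describe flyers, online advertisements, campus organisations, an eligibility survey, a baseline survey and randomisation. Neither mentions a check for earlier participation. On the comparator, Section 3.0 says: "The control group will be an assessment only control".

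**The concern.** Aim 3 recruits on the campus where the developmental phases have already run. Aim 2 enrolled heavy-drinking students from the same three risk groups and gave them ASAP. Aim 1b students reviewed its content in workbook form. Nothing in the stated rules keeps a former participant out of Aim 3. Such a student allocated to control has already seen the content, and one allocated to ASAP sees it a second time. In both arms the baseline survey would then be a post-exposure measurement.

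The protocol does not treat this kind of content as short-lived. Section 3.0 (sexual assault risk reduction component) credits programming on the same theoretical constructs with efficacy over follow-up of up to two years, and the Aim 3 outcomes are read at three months. The plan therefore gives no ground for assuming that earlier exposure is inert.

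At stake is the effect size that Aim 3 is meant to supply for planning the larger trial. An effect observed in a partly pre-exposed sample could understate the effect in students new to the programme. Later repair may be difficult, because the earlier Arizona State data are described as de-identified. Section 12.0 describes files linking names to identifiers, but the documents do not say whether such a list survives from the Arizona State phases.

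**Working it through.** **1. Can a former participant be randomised?**

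- Site: Aims 1b and 2 are reported as completed at Arizona State (Section 1.0), and Aim 3 runs only there.
- Drinking: Section 1.0 describes Aim 2 students as engaging in heavy episodic drinking. For the Arizona State Aim 1b students this is not stated.
- Aim 3 criteria: age, enrolment, email address and past-month drinking. Prior participation fails none of them.
- Exclusions: none beyond failing inclusion.

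So a former participant who still meets the four criteria is eligible for either arm.

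**2. The plan's own figure.** The SAP goes from 132 to 162 (3 × 54) for 20% attrition. Dividing gives 132 / 0.80 = 165, and multiplying gives 132 × 1.2 = 158.4. Neither is exactly 162, but both are close. This point disputes no sample-size figure, and 162 is used only as the denominator.

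**3. Exposed pool (assumption).** Section 1.0 gives 30 students for Aim 2 (10 per risk group) and 5 students per risk group for Aim 1b (15), without saying whether these are per site. Taking both as Arizona State counts gives an upper bound of 30 + 15 = 45. Sections 5.0 and 6.0 also give 25 Aim 1b students, but for Georgia State, so that figure is not used.

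**4. Dilution formula.** Let D be the ASAP-versus-control effect in unexposed students and f the share of the 162 previously exposed, split evenly between arms in expectation. Let r be the share of D that exposed controls already carry and that a second exposure does not add. The contrast among exposed students is (1 − r)D, so the expected overall effect is

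(1 − f)D + f(1 − r)D = (1 − f·r)D.

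This assumes similar attrition in exposed and unexposed students.

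| Re-enrolled | f | r = 1 | r = 0.5 | r = 0 |
|---|---|---|---|---|
| 5 | 5/162 = 3.1% | 0.97 | 0.98 | 1.00 |
| 10 | 10/162 = 6.2% | 0.94 | 0.97 | 1.00 |
| 30 (all of Aim 2) | 30/162 = 18.5% | 0.81 | 0.91 | 1.00 |
| 45 (all of Aims 1b and 2) | 45/162 = 27.8% | 0.72 | 0.86 | 1.00 |

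Entries are the fraction of D that remains. The bottom row is the same within a single risk group, since 15/54 = 27.8%. With an exclusion in place, f = 0 and the fraction is 1.00.

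**5. Scale against the pilot's precision.** With 20% attrition, 162 × 0.80 = 129.6 remain, or about 65 per arm if allocation is 1:1 (the ratio is not stated). The 95% half-width for a standardised difference is about 1.96 × √(2/65) = 0.34. For an assumed true difference of 0.3 standard deviations, a 6.2% loss is 0.3 × 0.062 = 0.02 and the 27.8% extreme is 0.3 × 0.278 = 0.08.

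**The case against.** A reader might infer that the missing exclusion biases the Aim 3 effect toward zero. The documents do not support that as a statement of fact. Randomisation spreads prior exposure over both arms in expectation, so the comparison remains unbiased for the sample actually enrolled. What can change is how far that effect represents unexposed students, and it falls only if former participants re-enrol, the earlier effect still acts, and a second exposure adds less than a first. The documents give no re-enrolment figure and no interval between the Arizona State phases and Aim 3.

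Other limits also stand:

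- The 45 is a ceiling built on unstated site counts, and it falls as students graduate or pass 25.
- Aim 1b was a workbook review with an interview, not the application. Section 3.0 describes the Aim 2 testing as preceding finalisation, with content revised on feedback. Treating both as a full earlier dose (r = 1) is therefore a worst case.
- That former participants would be readier to answer recruitment material is conjecture.
- The plausible loss is small beside the pilot's sampling error. The SAP sizes the study to estimate variability, and no harm to that estimate has been shown.
- The eligibility survey items are not reproduced, so a question on earlier participation could exist. Even so, the stated criteria would give staff no ground to act on the answer.

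One counter-argument fails. Section 5.0 lists only Georgia State criteria for Aims 1b and 2, but those lists cannot undo Section 1.0, which places completed cohorts for both aims at Arizona State.

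**Conclusion.** The gap is real and its consequence is conditional. As written, Aim 3 admits Arizona State students who have already seen the intervention or its workbook, including into a control meant to receive assessment only. If some re-enrol and their earlier effect persists without further gain from a second exposure, the observed effect is attenuated relative to unexposed students. The loss is about 3% to 6% for 5 to 10 re-enrolments and about 28% if the whole assumed pool of 45 returns. It is nil if earlier effects have faded or a second exposure adds as much as a first. A loss of a few percent is the more realistic order of size, though the documents do not allow it to be pinned down. This does not threaten the validity of the randomised comparison. It merits correction because the remedy is very cheap and the problem may be hard to detect afterwards.

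**What to change.** In Protocol Section 5.0, replace the blanket rule, as far as it concerns Aim 3, with: *Excluded from Aim 3: anyone who took part in Aim 1b or Aim 2 of this study.* Apply it through one yes/no item in the Aim 3 eligibility survey, which already precedes randomisation. A self-report item is needed because the earlier Arizona State data are held de-identified. Where a contact list from those phases still exists, check against it as well.

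The cost is one sentence and one survey item. At most about 45 students leave the recruitment pool, and some former participants may answer wrongly.

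If the investigators prefer not to narrow eligibility, the same item can be recorded before randomisation and the effect re-estimated without previously exposed students as a sensitivity analysis. That keeps the recruits but leaves the main estimate mixed.

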6.0 Number of Subjects

A total of 967 participants will be recruited (Aim 1a = 750 students from GSU, Aim 1b = 25 [25 students and 10 administrators] from GSU, Aim 2 = 30 students from GSU, Aim 3 = 162 students from ASU).

7.0 Setting

The research will be conducted at GSU.

8.0 Recruitment Methods

Aim 1a: A random sample of college students aged 18-25 enrolled at Georgia State University will be selected from the Georgia State University registrar list. Potential participants will be sent a recruitment email (see Recruitment email Aim 1a) to complete a 30-minute online survey. To ensure that there is adequate representation of participants across gender groups, potential participants will complete a brief screening survey prior to taking the baseline survey. Once enrollment across a single group is complete (n=250 women; n=250 men; n=250 sexual/gender minorities), further participation among that group will close, where participation will remain open for individuals of the other groups until enrollment goals are met (n=750).

Aim 1b: Participants will be recruited through SONA with an advertisement. Participants will be recruited to complete an online survey to determine eligibility (described above; Eligibility Survey), and a total of 5 students from each group (cisgender heterosexual male, cisgender heterosexual female, or sexual/gender minority) will be recruited to provide feedback on the workbook version of the intervention content during in-person one-on-one interviews.

Further, Georgia State University administrators will provide feedback on the workbook version of the content. Administrators will be recruited if they make either final or preliminary decisions regarding alcohol and/or sexual assault programming on the Arizona State University campus (e.g., Dean of Student Affairs, Title IX Coordinators).

Aim 2: Participants will be recruited from SONA using an advertisement on SONA. Participants will be recruited to complete an online survey to determine eligibility (described above; Eligibility survey), and a total of 10 students from each group (cisgender heterosexual male, cisgender heterosexual female, or sexual/gender minority) will be recruited to participate in an open pilot trial of the intervention (Recruitment Email Aim 2).

Aim 3: Participants will be recruited from flyers on campus, ads online, and from relevant campus organizations (no participants will be recruited until an inter-institutional agreement is signed by Arizona State University, submitted as an amendment to the GSU IRB and approved by the GSU IRB). Potential participants will email the study (e.g., [contact]) from an Arizona State University email address. Participants will be recruited to complete an online survey to determine eligibility (described above; Eligibility Survey), and a total of eligible 54 students from each group (cisgender heterosexual male, cisgender heterosexual female, or sexual/gender minority), for a total of 162 students will be recruited to participate in an open pilot trial of the intervention (Recruitment Email Aim 3).

9.0 Consent Process

Aim 1a: We are requesting a waiver of consent to conduct Aim 1a. All potential participants will be assigned a unique Personal Identification Number (PIN) that will be sent in the invitation email, and login information for completing the survey. Upon logging into the study website, potential participants will be presented with more information about the study (Aim 1a Information Statement). Upon reading about the study, they can decide if they want to continue or exit the survey. If they decide to continue, participants will be automatically re-directed to participate in the study. They will also be emailed the information statement for their records. If they decide to exit, we will ask if they'd like to be contacted for this study in the future or if they are not interested in the study. If they are not interested in the study, we will remove them from the reminder list.

Aim 1b: For Aim 1b, we are completing interviews in person. The interviewer, which will be an IRB-approved study staff member, will conduct the interview in a private office space. Study staff will obtain consent from the potential participant prior to beginning the study procedures. If a participant is not interested in participating after reviewing the consent document, they will not be enrolled in the study. Participants will have time to review the document, ask questions, and decide if they would like to give informed consent or not participate in the study.

Aim 2: A waiver of consent was applied for to conduct Aim 2. All interested eligible participants will be assigned a unique Personal Identification Number (PIN) that will be sent in an email to their Georgia State University email account which will include login information for completing the study. Upon logging into the study website, potential participants will be presented with more information about the study (Aim 2 Information Statement). Upon reading about the study, they can decide if they want to continue or exit the survey.

Aim 3: A waiver of consent was applied for to conduct Aim 3. All interested and eligible participants will be assigned a unique Personal Identification Number (PIN) that will be sent in an email to their Arizona

State University email account which will include login information for completing the study. Upon logging into the study website, potential participants will be presented with more information about the study (Aim 3 Information Statement). Upon reading about the study, they can decide if they want to continue or exit the survey.

10.0 Study Design / Methods

Aim 1a: Upon agreeing to participate in the study, participants will be automatically re-directed to complete a 30-minute online survey to assess campus norms to include in the intervention in subsequent study aims (see Aim 1a survey). Participants will have one month to complete the survey and will be sent reminder emails. Participants will be emailed a \$15 e-gift card for completing the study to their Arizona State University email account. Upon completing the survey, they will be given local resources regarding alcohol use, sexual assault, and mental health resources (see Resources). All participants will be given this information, regardless of their risk. Participants will be given the option of contacting the study staff if they are distressed by the study procedures. Members of the research team are licensed clinical psychologists and are well-equipped to follow-up with individuals in need. As been the case with our previous studies, we will establish a schedule in which members of the research team will be on call 24 hours a day, seven days a week to address urgent matters. If a participant is distressed and wishes to talk with a member of the research team, the clinical psychologist team member will be available at all times during the study period.

Aim 1b: Upon consenting to participate in the study, participants will complete the pre-interview survey (30-minute survey) using a study computer in a private room. Participants will then complete a 30-minute interview regarding the review content (Aim 1b interview script). Upon completing the interview, student participants will receive research credit, while Administrators/Staff will not receive compensation. Upon completing the interview, they will be given local resources regarding alcohol use, sexual assault, and mental health resources (see Resources). All participants will be given this information, regardless of their risk. Participants will be given the option of contacting the study staff if they are distressed by the study procedures. Members of the research team are licensed clinical psychologists and are well-equipped to follow-up with individuals in need. As been the case with our previous studies, we will establish a schedule in which members of the research team will be on call 24 hours a day, seven days a week to address urgent matters. If a participant is distressed and wishes to talk with a member of the research team, the clinical psychologist team member will be available at all times during the study period.

Aim 2: Upon agreeing to participate in the study, participants will be automatically directed to complete a 30-minute online survey regarding their demographics, alcohol use, sexual assault experiences, and bystander experiences and attitudes (Aim 2 Pre-Intervention Survey). Upon completing the survey, they will be automatically directed to receive the personalized feedback intervention (described above). This intervention will take approximately 15 minutes to complete (Aim 2 Post-Intervention Survey).

Immediately following the intervention, they will complete a 15-minute post-intervention survey regarding their feedback and immediate potential outcomes. Participants will receive research credit on SONA for completing the study. Upon completing the post-intervention survey, they will be given local resources regarding alcohol use, sexual assault, and mental health resources (see Resources). All participants will be given this information, regardless of their risk. Participants will be given the option of contacting the study staff if they are distressed by the study procedures. Members of the research team are licensed clinical psychologists and are well-equipped to follow-up with individuals in need. As been the case with our previous studies, we will establish a schedule in which members of the research team will be on call 24 hours a day, seven days a week to address urgent matters. If a participant is distressed and wishes to talk with a member of the research team, the clinical psychologist team member will be available at all times during the study period.

Aim 3: Upon agreeing to participate in the study, participants will be automatically re-directed to complete a 30-minute online survey regarding their demographics, alcohol use, sexual assault experiences, and bystander experiences and attitudes (Aim 3 Baseline Survey). Upon completing the survey, they will be randomly assigned to either receive the personalized feedback intervention (described above) or to an assessment only control condition. If they were assigned to receive the personalized feedback intervention, they will be automatically directed to receive the personalized feedback intervention (described above). This intervention will take approximately 15 minutes to complete. Immediately following the intervention, they will complete a 15-minute post-intervention survey regarding their feedback and immediate potential outcomes (post-intervention survey). A total of 162 eligible participants will be paid \$25 for completing the baseline portion of the study. Upon completing the post-intervention survey, they will be given local resources regarding alcohol use, sexual assault, and mental health resources (see Resources). All participants will be given this information, regardless of their risk. Participants will be given the option of contacting the study staff if they are distressed by the study procedures. Members of the research team are licensed clinical psychologists and are well-equipped to follow-up with individuals in need. As been the case with our previous studies, we will establish a schedule in which members of the research team will be on call 24 hours a day, seven days a week to address urgent matters. If a participant is distressed and wishes to talk with a member of the research team, the clinical psychologist team member will be available at all times during the study period. The procedure will be the same for Arizona State University student and administrator participants except student participants will be compensated for their time and administrators will be volunteering their time.

Participants will be contacted 3 months after completing the initial survey in an email (Aim 3 Follow-Up Email) with their PIN. The follow-up survey will be exactly the same as the baseline survey, except time periods will include the “past 3 months” for questions. Participants will have one month to complete the survey and will be sent reminder emails if they have not completed the survey. Upon completing the survey, they will be emailed an e-gift card for \$35 for completing the survey. Upon completing the survey, they will be given local resources regarding alcohol use, sexual assault, and mental health resources (see Resources). All participants will be given this information, regardless of their risk. Participants will be given the option of contacting the study staff if they are distressed by the study procedures. Members of the research team are licensed clinical psychologists and are well-equipped to follow-up with individuals in need. As been the case with our previous studies, we will establish a schedule in which members of the research team will be on call 24 hours a day, seven days a week to address urgent matters. If a participant is distressed and wishes to talk with a member of the research team, the clinical psychologist team member will be available at all times during the study period. The procedure will be the same for Arizona State University student and administrator participants except student participants will be compensated for their time and administrators will be volunteering their time.

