To minimize distress or discomfort associated with participation in the study (from either assessment or the intervention): (a) participants will be informed that they can discontinue participation at any time; and (b) if other problems arise, a licensed psychologist will be available to address the distress. Upon completing the survey, they will be given local resources regarding alcohol use, sexual assault, and mental health resources (see Resources). All participants will be given this information, regardless of their risk. Participants will be given the option of contacting the study staff if they are distressed by the study procedures. Members of the research team are licensed clinical psychologists and are well-equipped to follow-up with individuals in need. As been the case with our previous studies, we will establish a schedule in which members of the research team will be on call 24 hours a day, seven days a week to address urgent matters. If a participant is distressed and wishes to talk with a member of the research team, the clinical psychologist team member will be available at all times during the study period.

A detailed safety plan - detailing what to do and whom to speak with if ideation should occur - will be included in standard referral information provided to all participants, including specifics on how to access 24-hour care for suicidality via dialing 9-1-1 and/or going to the closest emergency department when a PI is not available. Thus, a 24-hour safety plan is in place, including access to medical care 24 hours per day. Further, any participant in which it is deemed that medication is warranted will be referred to a psychiatrist for such services and monitoring. Suicidal risk factors - including suicidal ideation, intent, plan, and means - will continue to be assessed on an ongoing basis throughout the students' participation

in the study for those who are participating in the open and randomized pilot trial.

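### Aim 3: a participant who stops during the baseline survey is reached by no timed step for giving out the resource sheet, because every such step waits for a completed survey

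*Protocol*

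**What the plan says.** Three statements in the Protocol that apply to Aim 3 give a time for handing over the sheet of local resources.

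- Section 10.0, Aim 3 baseline session: "Upon completing the post-intervention survey, they will be given local resources regarding alcohol use, sexual assault".
- Section 10.0, Aim 3 follow-up at month 3: "Upon completing the survey, they will be given local resources regarding alcohol use, sexual assault, and mental health resources".
- Section 15.0, Protection Against Risk, uses the same completion wording without naming an aim or a survey.

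Each is followed by a general commitment: "All participants will be given this information, regardless of their risk". Section 15.0 adds that a safety plan for suicidal ideation "will be included in standard referral information provided to all participants", with no time stated.

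Section 15.0 also lists, as its first measure against distress, that "participants will be informed that they can discontinue participation at any time". Section 14.0 describes withdrawal: the participant tells the study, and the study removes the data or stops contact. It does not mention resources.

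On the sequence of events, section 10.0 says of the baseline survey: "Upon completing the survey, they will be randomly assigned". On follow-up it says: "Participants will be contacted 3 months after completing the initial survey in an email".

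**The concern.** The plan offers stopping as a protection, yet attaches the sheet to not stopping. The Aim 3 baseline survey takes 30 minutes and covers the participant's own sexual assault experiences. Section 15.0 itself says that a small number of people report distress after this kind of assessment, and that suicidality is a risk of victimization. A student who leaves because the questions upset them is someone for whom the sheet exists. If delivery waits for the last screen, that student may leave without it.

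What is at stake is participant protection, and whether the procedure carries out the plan's own commitment to give the sheet to everyone. No estimate or test is affected.

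**Working it through.** No formula applies, and the plan gives no figure to reproduce. The check compares each timed statement with each point at which a participant could stop for good.

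| Participant | Section 10.0, baseline session | Section 10.0, month 3 | Section 15.0 |
|---|---|---|---|
| Stops during the baseline survey | Not met | Not contacted | Not met |
| ASAP arm, finishes the baseline survey, stops during the intervention or post-intervention survey | Not met | Met if the follow-up survey is finished | Met, if the survey meant is the baseline survey |
| ASAP arm, finishes the baseline session, stops during the follow-up survey | Already met | Not met | Already met |
| Control, finishes the baseline survey | Has no such survey | Met if the follow-up survey is finished | Met |

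**Baseline exit.** Randomization comes only after the baseline survey is completed, so this person never reaches the intervention or the post-intervention survey. The month-3 email is timed from completion of the initial survey, so there is no later contact at which the sheet could be given. All 3 timed statements require completion, and 0 of 3 reach this person. The section 15.0 statement is a general restatement rather than a separate Aim 3 step, so the count describes the text and is not a measure of size.

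**Earliest trigger.** On the section 15.0 wording, the sheet can appear at the end of the 30-minute baseline survey. On the section 10.0 wording, it appears in the ASAP arm after the survey, the intervention and the post-intervention survey: 30 + 15 + 15 = 60 minutes. On either reading nothing is scheduled before minute 30.

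**Controls.** Section 3.0 (Control Group) gives controls an assessment and no intervention, and section 10.0 describes the post-intervention survey only as following the intervention. The baseline-session trigger therefore does not fit them. The sentence covering all participants and the arm-neutral wording of section 15.0 show that they are meant to receive the sheet.

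**The case against.** The strongest reply is that a scheduled moment is being read as an exclusive condition. The plan says that all participants get the information, and it places the safety plan in referral material for everyone. It pairs the freedom to stop with a licensed psychologist, on call at all hours, and with an invitation to contact staff; neither depends on finishing a survey. Suicidality is to be assessed throughout participation in the randomized pilot. Section 15.0 also offers referrals to students who choose not to take part. Section 9.0 has everyone see an Aim 3 Information Statement before the survey. That statement, the Resources attachment and the survey itself are not in the documents, and a data and safety monitoring plan is to follow by amendment (section 13.0). Any of these could list contacts or define an exit page. The Protocol also rates the study as minimal risk.

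Much of this stands. The intent to reach everyone is written, and real protections exist without completion. What remains is narrower. The commitment to all participants adds neither a time nor a mechanism to the completion sentence before it. The referral information has no time. Staff and psychologist contact must be started by the distressed person. The method of suicidality assessment after someone has stopped is not given. The referrals for non-participants are described in connection with advertising the study.

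A reader might infer that anyone who stops partway, at any stage, misses the sheet. The documents do not support that: the later exits in the table are largely covered by the section 15.0 wording, the baseline session or the month-3 survey.

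**Conclusion.** The gap is real but confined to people who stop during the Aim 3 baseline survey and do not return to finish it. For them no timed step delivers the sheet. It is a cheap improvement of low severity, because several protections do not depend on completion.

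Its size cannot be estimated. A reader might take the 20% attrition in the SAP as a guide. That figure is loss over the 3-month follow-up, whereas baseline exits occur before randomization. It also includes people who never open the follow-up survey, and most of those lost at that stage should already have had the sheet.

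A reader might also infer that controls would be missed. The documents do not show this; the control-arm issue is a trigger worded for the other arm.

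The conclusion assumes that the unseen Information Statement and survey screens do not already show the resources. If the Information Statement lists them, a person who leaves during the baseline survey has seen them, and little beyond rewording is needed.

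**What to change.** Amend the two Aim 3 paragraphs of section 10.0 and the Protection Against Risk text in section 15.0 as follows.

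1. Make the resource and safety-plan page available to both arms from the first screen of each survey, through a persistent link on every screen.
2. Show the same page on early exit as well as on completion.
3. Replace the baseline-session trigger with one that fits both arms: the end of the post-intervention survey for ASAP, and the end of the baseline survey for controls.
4. State in section 15.0 that the safety plan is given at these same points.

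I would not add an email to people who leave a survey unfinished. Section 12.0 keeps identifiers apart from survey data, so staff would have to re-link them in order to send sensitive material to someone who has chosen to stop. The persistent link is available without that step, even to someone who simply closes the browser.

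The cost is minor survey routing and a sentence in each of the three places. The one downside is that a standing link on a sensitive survey needs neutral wording, in case someone else sees the screen. Both arms receive the same page, and sample size and analysis do not change.
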